10.6.2.2. Demographic & Baseline Characteristics

Demographic & Baseline Characteristics

Age

- GSK standard IDSL algorithms will be used for calculating age where birth date will be imputed as follows:
 - \circ Any subject with a missing day will have this imputed as day '15'.
 - o Any subject with a missing date and month will have this imputed as '30th June'.

200807

Demographic & Baseline Characteristics
 Birth date will be presented in listings as 'YYYY'.
High Level Race
~
 Geographic ancestry data will be combined into the following high level race categories: American Indian or Alaskan Native
 Aniencan indian of Alaskan Native Asian (Asian-East Asian Heritage, Asian-Japanese Heritage, Asian-Central/South
Asian Heritage, Asian-South East Asian Heritage, Mixed Asian Race)
 Black or African American
• Native Hawaiian or Other Pacific Islander
 White (White-Arabic/North African Heritage, White-White/Caucasian/European Heritage, Mixed White Race)
 Mixed Race (Multiple high level races are selected)
Note: A subject will only be counted in one category. Mixed Asian Race includes subjects who have more than one Asian category selected, but no other categories. Mixed White Race includes subjects who have more than one White category selected, but no other categories.
Race Detail
Geographic ancestry data will be combined into race detail categories:
 American Indian or Alaskan Native
 Asian-Central/South Asian Heritage
 Asian-East Asian Heritage
 Asian-Japanese Heritage
 Asian-South East Asian Heritage
 Mixed Asian Race (Only display if data exists)
 Black or African American (African American/African Heritage)
 Native Hawaiian or Other Pacific Islander
 White-Arabic/North African Heritage
 White-White/Caucasian/European Heritage
 Mixed White Race (Only display if data exists)
 Mixed Race (Multiple high level races are selected; only display if data exists)
Note: A subject will only be counted in one category. Mixed Asian Race includes subjects who
have more than one Asian category selected, but no other categories. Mixed White Race includes
subjects who have more than one White category selected, but no other categories.
Dialysis Type at Randomization
 Dialysis type at randomization will use the subject's randomization date and the dialysis type information recorded on the Dialysis History and Dialysis Changes eCRF pages to determine the dialysis type on the randomization date and will be summarized as follows: HD (which includes: HD – conventional and HDF/HF) PD Missing
Prior ESA Type and Standardized Prior ESA Dose (U/week) at Randomization
 During the screening period, subjects may be receiving ESAs in multiple ways, including: epoetin IV or SC, darbepoetin IV or SC, or methoxy PEG-epoetin beta IV or SC.
• A subject's prior ESA type will be determined from the records that contribute to the subject's standardized prior ESA dose. The following categories of prior ESA type will be summarized:

Demographic & Baseline Characte	eristics	
 Darbepoetin alfa on 	у	
• •	contains subjects using any of the f , epoetin beta, epoetin lambda, epo	
 Methoxy PEG-epoe 	tin beta only	
	contains subjects using methoxy Pl	EG-epoetin beta and
o Multiple		
U	contains subjects using any combir	nation of the ESA types.
 Missing 		
terms of epoetin IV U/week for th Randomization date.	dized to obtain a continuous single ne period from the Week -8 visit to t nt medication records from screenin	the day before the
and ordered by start date and er		0
 For subjects taking epoetin SC: Standardized ESA of For subjects taking darbepoetin Standardized ESA of For subjects taking methoxy PEO Standardized ESA of (µg)*frequency Note: Frequency and Gap Factorian Standardized ESA of (µg) 	lose (U/week) = epoetin IV dose (U lose (U/week) = (161/113)*epoetin IV or SC: lose (U/week) = 250*darbepoetin d G-epoetin beta: lose (U/week) = 208*methoxy PEG	SC dose(units)*frequency ose (µg)*frequency -epoetin beta dose
Frequency (from eCRF)	(for standardization formula)	Gap Factor
One time dose	see below	n/a
Four times per week	4	0.75 day
Three times per week	3	1.33 days
Two times per week	2	2.5 days
Every week	1	6 days
Every 10 days	0.70	9 days
Every 2 weeks	0.50	13 days
Every 3 weeks	0.33	20 days

200807

Every 4 weeks	
Every 5 weeks Every 6 weeks	
 the frequency of the record is a one of the concomitant media the record is 0. If the concomitant media duration of the record is If the concomitant media duration of a record will Start date will b the Week -8 vis Stop date will b the Week -8 vis Stop date will b the frequency of the record is 0. If the concomitant medic the record is 0. If Week -8 visit date ≤ c Frequency (for a Duration = 7 da If concomitant medication Frequency (for a Sequential prior before randomization) If the earliest not ESA concomitant randomization) If the earliest not ESA concomitant randomization Stop Date – State Stop date and the stop	

Mean prior ESA dose = [(ESA total dose_{Record 1}) + ... Randomization Date – Week -8 Visit Date)/7days]

200807

	mographic & Baseline Characteristics
Ba	seline Erythropoietin Resistance Index (ERI, U/kg/wk/g/L)
•	Calculated by dividing the standardized prior ESA dose (U/week) at randomization by the baseline estimated dry weight (in kg) and then dividing by the achieved Day 1 Hgb (in g/L). Note: the central laboratory Hgb value from Day 1 should be used to calculate ERI, however if this value is missing and there is a corresponding non-missing HemoCue Hgb value available, the Day 1 HemoCue Hgb value will be used.
rhE	PO Hyporesponders
•	 A subject will be considered to be a hyporesponder if: ○ ERI ≥ 2.0 U/kg/wk/g/L Or ○ Prior ESA dose (U/week) at baseline divided by the baseline estimated dry weight (in kg) ≥ 450 U/kg/week
•	Note: an ERI \geq 2.0 U/kg/wk/g/L for epoetin-treated subjects corresponds to an ERI \geq 0.008µg/kg/wk/g/L for darbepoetin-treated subjects and \geq 0.01 µg/kg/wk/g/L for methoxy-PEG-epoetin-treated subjects.
•	Supportive analyses will be used in the summary of demographics and baseline characteristics and will use the following alternative hyporesponder definitions: 1) an ERI cut-point of \geq 1.5 U/kg/wk/g/L only
	2) subjects with prior ESA dose (U/week) at baseline in the top 20 th percentile of the randomized study population.
Ba	seline Post-Dialysis Body Mass Index (BMI)
•	Calculated as baseline post-dialysis weight (kg) / [height (m)] ²
Do	sing Algorithm at Randomization
•	Protocol Amendment 3 updated the dosing algorithm used to assign doses of randomized treatment to subjects in both treatment arms. The number of subjects randomized under the original algorithm and under the updated algorithm will be summarized. A subject's randomization date will be compared to the site-specific ethics committee/regulatory protocol amendment approval date for their site. This date is stored in the IRT system as the Site Level Amendment Flag Date for each site. Subjects randomized before their site's non-missing Site Level Amendment Flag Date or who have a missing Site Level Amendment Flag Date will be considered to have been randomized under the original algorithm, and subjects randomized on or after their site's non-missing Site Level Amendment Flag Date will be considered to have been randomized under the updated algorithm.
Ca	rdiovascular Risk Score
	sk score for two-year cardiovascular mortality and morbidity in a hemodialysis population has an developed [Anker, 2016] and will be calculated at baseline for each HD participant.
The	e following table describes how the published risk score is calculated*:

200807

Demographic & Baseline Ch		S sk Score For Patients on Chronic Hemo	dialveie
Parameter (unit) and values	Risk Score Points	sk Score Parameter (unit) and values	
Age [years]		Intradialytic Weight Change [kg]	
≤39	CCI	< -2.2	CCI
40 to 49		-2.2 to < -1.7	
50 to 59		-1.7 to < -1.2	
60 to 69		> -1.2	
70 to 79		Haemoglobin [g/L]	
≥80		<100	
Smoking Status:		100 to <120	
Current		≥120	
Former		Reactive Protein [mg/L]	
Nonsmoker		< 2.4	
CVD history		2.4 to < 6.8	
Yes		6.8 to < 18.0	
No		≥ 18.0	
Pre-dialysis SBP [mmHg]		Serum Albumin [g/L]	
<120		<35	
120 to <130		≥35	
130 to <140		Creatinine [µmol/L]	_
140 to <160		< 436	
≥160		436 to < 542	
CKD Aetiology:		542 to < 678	
Hypertension/vascular		≥ 678	
Glomerulonephritis		Calcium [mmol/L]	
Diabetes		<2.1	
Tubulo-interstitial		2.1 to <2.6	
Polycystic Kidney Disease		≥2.6	
Unknown renal diagnosis		Total Cumulated Risk Points	

*For the intradialytic weight change (kg) parameter, a value of \geq -1.2kg will have a risk score of 0 points.

It should be noted that creatinine is not routinely collected in this study and will be assumed to be the same in all HD participants (i.e. <436, resulting in 3 risk score points).

CVD history is defined as having a yes response to any of the following medical history conditions: angina pectoris, myocardial infarction, stroke, coronary artery disease, transient ischaemic attack, heart failure, atrial fibrillation, cardiac arrest, valvular heart disease.

Intradialytic weight change will be calculated using the Week -4 post-dialysis weight in kg – the Week -4 pre-dialysis weight in kg.

Baseline Hgb categories will be defined based on g/dL units (i.e. <10, 10-<12 and \geq 12) and will use central laboratory Hgb values if available. If a baseline central laboratory Hgb value is not available, a baseline HemoCue Hgb value will be used.

Risk score points for CKD aetiology will be determined based on the following approach:

- i. Participants with diabetic renal disease are assigned 4 points
- ii. All other participants who have hypertensive renal disease are assigned 1 point

Demographic & Baseline Characteristics	
iii. All other participants who have interstitial nephritis are assigned -	•
iv. All other participants who have a medical history of polycystic kid	
or do not have any of these medical history terms selected are as	ssigned 0 points
The overall CV risk score is determined by summing up the individual risk factors.	scores for the 11 risk
History of Diabetes	
 Subjects are considered to have a history of diabetes if they have a y one record of the medical history terms that contains "Diabetic" or "Di containing non-diabetic or variations relating to it (e.g. nondiabetic an also: 	iabetes" except anything
 DIABETES INSIPIDUS, 	
 NEPHROGENIC DIABETES INSIPIDUS 	
 If subjects have indicated that they do not have any of the listed diable conditions above, they are considered not to have a history of diabeted 	•
 If subjects have not been classified as either having or not having a h missing a response to any of the listed medical history conditions, the will be missing. 	
History of Stroke	
 Subjects are considered to have a history of stroke if they have a yes medical history condition. 	s response to the stroke
 Subjects who have indicated that they do not have a history of stroke accordingly. 	will be summarized
 If a subject is missing a response to the stroke medical history condit status will be missing. 	ion, their stroke history
History of MI	
 Subjects are considered to have a history of MI if they have a yes res following medical history conditions: myocardial infarction, cardiac and 	•
• Subjects who have indicated that they do not have a medical history of cardiac arrest will be considered not to have a history of MI.	of myocardial infarction or
 If subjects have not been classified as either having or not having a h missing a response to either the myocardial infarction or cardiac arres MI history status will be missing. 	
History of Cancer	
 Subjects are considered to have a history of cancer if they have a yes following medical history conditions: neoplasms malignant or unknow bone marrow transplant. 	
 Subjects who have indicated that they do not have a medical history of unknown/unspecified or allogenic bone marrow transplant will be con history of cancer. 	
 If subjects have not been classified as either having or not having a h missing a response to either the neoplasms malignant or unknown/un bone marrow transplant medical condition, their cancer history status 	nspecified or allogenic

Demographie & Recelling Characteristics
Demographic & Baseline Characteristics
History of Heart Failure
• Subjects are considered to have a history of heart failure if they have a yes response to any of the following medical history conditions: heart failure, left ventricular systolic dysfunction, left ventricular diastolic dysfunction, pulmonary hypertension.
• Subjects who have indicated that they do not have a medical history of any of the terms listed above will be considered not to have a history of heart failure.
 If subjects have not been classified as either having or not having a history of heart failure and are missing a response to any of the medical condition terms listed above, their heart failure history status will be missing.
History of Thromboembolic Events
 Subjects are considered to have a history of thromboembolic events if they have a yes response to any of the following medical history conditions: pulmonary embolism, deep vein thrombosis, retinal vein occlusion, arteriovenous graft thrombosis, arteriovenous fistula thrombosis, central venous catheter thrombosis. Subjects who have indicated that they do not have a medical history of any of the terms listed above will be considered not to have a bistory of thrombosing currents.
 above will be considered not to have a history of thromboembolic events. If subjects have not been classified as either having or not having a history of thromboembolic events and are missing a response to any of the medical condition terms listed above, their thromboembolic event history status will be missing.
History of Cardiovascular Disease
• Subjects are considered to have a history of cardiovascular disease if they have a yes response to any of the following medical history conditions: angina pectoris, myocardial infarction, stroke, coronary artery disease, transient ischaemic attack, heart failure, atrial fibrillation, cardiac arrest, valvular heart disease.
• Subjects who have indicated that they do not have a medical history of any of the terms listed above will be considered not to have a history of cardiovascular disease.
• If subjects have not been classified as either having or not having a history of cardiovascular disease and are missing a response to any of the medical condition terms listed above, their cardiovascular disease history status will be missing.
Baseline Iron Use & Standardized Baseline IV Iron Dose
See Section 10.6.3.
Dialysis Access Type Used at Randomization
 Dialysis access type at randomization will use the subject's randomization date and the dialysis access type information recorded on the Dialysis Access History and Dialysis Access Changes eCRF pages to determine the dialysis access type on the randomization date and will be summarized as follows: Arteriovenous fistula
 Arteriovenous graft
 Central venous catheter – tunneled
 Central venous catheter – non-tunneled
 Peritoneal catheter
○ Other
○ Missing

200807

	200807
Demographic	& Baseline Characteristics
Phosphate B	nder Use at Randomization
Phosphate	e binder use at randomization will be summarized as follows:
0	Iron-based phosphate binders
0	Calcium-based phosphate binders
0	Non-calcium and non-iron based phosphate binders
0	No phosphate binder use
	vill be counted in each applicable group, based on the concomitant medications they ing on the day of randomization.
Concomitant	Medication Use at Randomization
	ant medication records on the day of randomization will be used to determine the classifications of concomitant medication use at randomization:
0	
0	
0	Beta blockers
0	SGLT2i
0	
0	Aspirin
0	
0	Insulin
0	
0	Diabetic medication
	Randomized Treatment Discontinuation, Study Withdrawal and Possible Follow-up Time
	Treatment Discontinuation, Study Withdrawal, and Possible Follow-up Time
Randomized	Treatment Discontinuation
Treatment	ed Treatment Discontinuation Censored Time (days) = Treatment stop date – : start date +1
	It stop date = death date for a subject, the subject will be censored and will not be event for treatment discontinuation summaries that exclude subjects who die while

- Time to Randomized Treatment Discontinuation (days) = Treatment stop date Treatment start date +1
- Randomized Treatment Person Years = (Cumulative total of time to randomized treatment discontinuation for subjects who discontinued randomized treatment + Cumulative total of randomized treatment discontinuation censoring time for subjects who did not discontinue randomized treatment) / 365.25
- Randomized Treatment Discontinuation Incidence Rate (per 100 person years) = 100* Number of subjects who discontinued randomized treatment / randomized treatment person years

Study Withdrawal

- Study Censored Time (days) = Study completion date Randomization date +1
- Time to Study Withdrawal (days) = Study withdrawal date Randomization date +1

200807

Randomized Treatment Discontinuation, Study Withdrawal, and Possible Follow-up T	ime
--	-----

- Study Person Years = (Cumulative total time to study withdrawal for subjects withdrawing from the study + Cumulative total of study censoring time for subjects who did not withdraw from study) / 365.25
- Study Withdrawal Incidence Rate (per 100 person years) = (100 * Number of subjects who have withdrawn from study) / Study Person Years

Possible Follow-up Time

- Possible follow-up time (days) = Study completion date or date of the middle of the end of study window for subjects who did not complete the study randomization date + 1
- Total possible follow-up time (person years) = Cumulative total of possible follow-up time (days) for all subjects / 365.25

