Two Kaplan-Meier plots of time to permanent randomized treatment discontinuation by treatment group will be produced. For both of the plots, the risk set will include all subjects who started taking randomized treatment. The first plot will consider an event as subjects who discontinued randomized treatment and the second plot will consider an event as subjects who discontinued randomized treatment and did not die while on treatment. If a subject discontinued treatment due to death, that subject will not count towards the event, and will be censored instead.

The number and percentage of subjects by region, country, site ID and investigator name will be summarized by treatment group and overall for the enrolled population.

The type of subject contact at the Week 28, Week 52 visit and End of Study visit will be provided by treatment group and overall.

A summary of the timing of the end of study contact will be provided by subject status, type of contact, treatment group and overall.

A summary of the total follow-up time and percentage of total possible follow-up time during time periods of the study (i.e., time period for follow-up of CV endpoints, time period for vital status, and time period for on-treatment CV endpoints) will be provided by treatment group and overall (see Section 10.6.2 and Section 10.6.4 for definitions). Cardiovascular Endpoint Follow-up Among All Randomized Subjects will be presented by a figure.

A summary of the subject completion status, including the number and percentage of subjects included in the co-primary Hgb analysis, by CV endpoint status (known and unknown at the end of study) and by vital status (known and unknown at the end of study) will be provided by treatment group and overall.

A summary of the subject survival status by study completion status will be provided by treatment group and overall.

A listing of planned and actual treatments will be provided. This listing will include region, country, site ID, investigator name, subject number, randomization number, randomization date, randomized treatment, actual treatment flag.

6.2.3. **Protocol Deviations**

The number and percentage of subjects who had significant protocol deviations (defined in PPD's Study Deviation Rules Document) will be summarized by category and by treatment group and overall. It will be repeated by relationship to COVID-19 pandemic.

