• •	• Calculated as the latest randomized treatment dose stop date, for subjects who have a non- missing treatment start date. Note that this date could come from a randomized treatment exposure record with a missing or partial dose stop date if the associated dose start date for that exposure record is on or after the last non-missing randomized treatment dose stop date.			
	 '31' will be used for the day and 'Dec' will be used for the month, unless the study completion or withdrawal date also occurs in the same year; in this case, the study completion or withdrawal date will be used. Missing day, month and year: The study completion or withdrawal date will be used only for subjects 			
	who have a non-missing treatment start date.			
End	of Treatment Value			
	 Only defined for subjects with a non-missing treatment start date Hgb, iron, transfusion and PRO parameters: the latest value on or before the treatment stop date + 1 day. Blood pressure, central laboratory, and vital signs parameters: the latest value on or before the last non-zero dose date + 1 day. 			
Stud	ly Completion/Withdrawal Date			
	 Date of withdrawal for subjects withdrawing (i.e., subjects who actively withdraw or are deemed lost to follow-up) from study or date of completion of study for subjects who complete the study. If the date of study withdrawal entered in the eCRF is before the last study contact date, the last study contact date will be used as the study withdrawal date for analysis. 			
	 Note: Subjects who die while on study are considered as having completed the study 			
	 The eCRF allows for the possibility of missing or partial dates to be recorded for the study completion/withdrawal date on the Study Conclusion form (i.e., missing day, or day and month, or day and month and year). In such a case, or in case of subjects who are missing a Study Conclusion form, the following conventions will be applied in order to impute a study completion/withdrawal date: Missing day: 			
	 The last day of the month will be used, unless the last study contact date also occurs in the same month; in the case, the last study contact date will be used. 			

200807

the last study contact date also or last study contact date will be use	Dec' will be used for the month, unless ccurs in the same year; in this case, the ed.
 Missing day, month and year: The last study contact date will be 	
Planned/Actual Visit Dates	
Planned/actual visit dates will be defined as follow	

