 First event incidence rate (per 100 person years) = (100 * number of subjects with at least 1 event) / first event person years
• First event absolute rate difference (per 100 person years) = daprodustat incidence rate (per 100 person years) – rhEPO incidence rate (per 100 person years)
Evaluation Time Periods for CV Endpoints
Time Period for Follow-up of Cardiovascular Endpoints
The period for capturing CV safety endpoints begins at randomization. The end of this time period is the date of study completion/withdrawal, with the exception that if a death has been reported in the clinical database after this time, then the death will be included in the analysis.
Any endpoints that occurred before the start of this time period are considered to be prior to the time period for follow-up of cardiovascular safety events, and any endpoints that occurred after the end of this time period are considered to be post the time period for follow-up of cardiovascular safety endpoints.
Time Period for Vital Status
The period for capturing vital status begins at the date of randomization. The end of this time period is defined as follows:
For all subjects known to have died, use the date of death
• For all subjects who complete the study, use the study completion date (see Section 10.6.1)
• For all subjects who withdraw from the study, but vital status has been ascertained, and are known to have not died – use the latest date last known to be alive. If vital status has not been ascertained following study withdrawal, use the study withdrawal date
Any endpoints that occurred before the start of this time period are considered to be prior to the time period for vital status, and any endpoints that occurred after the end of this time period are considered to be post the time period for vital status.
Time Period for On-treatment Cardiovascular Endpoints
The period for capturing on-treatment CV safety endpoint events begins at the treatment start date The end of this time period is defined as follows:
 For subjects whose last non-zero dose date is missing and who took randomized treatment, use date of study withdrawal/completion
 For subjects continuing on study past the last non-zero dose date +28 days, use (last non-zero dose date + 28)
 For subjects whose study withdrawal/completion date is on or before (last non-zero dose date +28), use date of study withdrawal/completion

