If the censoring date as defined above for on-treatment CV safety endpoints is after the censoring date as defined for the primary analysis during the time period for follow-up of CV safety endpoints

200807

CV Safety Endpoints

then use the censoring date for the primary analysis time period.

Any endpoints that occurred before the start of this time period are considered to be prior to the time period for on-treatment cardiovascular safety endpoints, and any endpoints that occurred after the end of this time period are considered to be post the time period for on-treatment cardiovascular safety endpoints.

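### Possible follow-up for a withdrawn subject runs past a known death, and vital-status time for withdrawn survivors has no cap, so the vital-status percentage of possible follow-up is distorted whenever such subjects occur

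*SAP*

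**What the plan says.** Section 6.2.2 commits to a summary of total follow-up and the "percentage of total possible follow-up time during time periods of the study", for three periods: CV endpoints, vital status and on-treatment CV endpoints. It is shown by arm and overall. Section 8.6 lists this table (1.017) among those repeated without the three sites closed for GCP issues.

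**Denominator.** The possible follow-up definition in Section 10.6.2 (between 10.6.2.2 and 10.6.2.4) starts at randomization. It ends at the study completion date, or at the "date of the middle of the end of study window for subjects who did not complete the study". Section 10.6.1 gives a "date of completion of study for subjects who complete the study" and notes: "Subjects who die while on study are considered as having completed the study". Section 10.7.1 repeats that exception.

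**Numerators (Section 10.6.4.1).**
- Vital status: "For all subjects known to have died, use the date of death". For withdrawn subjects known not to have died, "use the latest date last known to be alive".
- CV endpoints: the period ends at completion or withdrawal, except that "if a death has been reported in the clinical database after this time, then the death will be included in the analysis".
- On-treatment CV endpoints: if the derived end falls later than the primary one, "use the censoring date for the primary analysis time period".

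**Status classes.** Section 10.6.2.1 treats vital status as known for anyone with a death date. For withdrawn subjects it treats it as unknown when the last date known alive falls before the end-of-study window. Withdrawal puts a subject in the unknown class for CV endpoint status.

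**The concern.** Two subjects with the same complete information on survival are scored differently. If death occurs on study, the subject is a completer and possible time stops in effect at death. If death occurs after withdrawal but is known, possible time continues to the middle of the end-of-study window. The subject is then scored as having incomplete vital-status follow-up, although the SAP itself calls the status known.

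The opposite error arises for withdrawn subjects traced alive. Their possible time ends at the middle of the window and their observed time does not. A contact in the second half of the window, or after it, gives more than 100% for that subject and can offset time truly missing in others.

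At stake is a completeness figure that readers of an event-driven, open-label non-inferiority trial will consult when they judge the MACE result. SAP Section 10.6.2.3 and Section 10.6.4.1 should therefore use the same end date.

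**Working it through.** The SAP states no percentage, number withdrawn or number of deaths after withdrawal for this point, so there is no figure to reproduce. Section 6.2.2 does not write out the ratio. I take it as

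percentage = 100 × observed time (10.6.4.1) / possible time (10.6.2).

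**Single subjects.** Assume the middle of the end-of-study window is day 1000.

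| Subject | Period | SAP rules | Ends aligned |
|---|---|---|---|
| Dies on study, day 400 | Vital status | 400/400 = 100% | 400/400 = 100% |
| Withdraws day 200, known death day 400 | Vital status | 400/1000 = 40% | 400/400 = 100% |
| Withdraws day 200, last known alive day 1020 | Vital status | 1020/1000 = 102% | 1000/1000 = 100% |
| Withdraws day 200, known death day 400 | CV endpoints | 200/1000 = 20%, or 400/1000 = 40% if time is counted to the death | 200/400 = 50% |

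The 100% in the top row takes the completion date of an on-study death to be the death date. The SAP implies this but does not write it.

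The last row needs care. Moving both ends to the death would give 400/400 = 100%, although MI and stroke were not ascertained from day 200 to day 400. The right CV figure keeps observed time at withdrawal, hence 50%.

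**Cohort, vital status.** Let w be the share who withdraw, f the share of these with a known later death, g the fraction of possible time at which that death falls, h the fraction of possible time to which the other withdrawn subjects are known alive, and c the mean completer time relative to the maximum. Vital status is otherwise complete, so the aligned figure is 100%. Under the SAP:

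percentage = 100 × [(1−w)c + w(fg + (1−f)h)] / [(1−w)c + w].

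Assumed ranges, none of them from the SAP: w 2–10%, f 10–40%, g 0.4–0.6, h 1.00–1.02, c 0.9.

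- Smallest distortion (w 0.02, f 0.1, g 0.6, h 1.02): (0.882 + 0.02 × 0.978)/0.902 = 0.90156/0.902 = 99.95%.
- Largest distortion (w 0.10, f 0.4, g 0.4, h 1.00): (0.81 + 0.10 × 0.76)/0.91 = 0.886/0.91 = 97.36%.

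The net understatement is therefore 0.05 to 2.64 percentage points over these ranges. The sign is not fixed. With no deaths after withdrawal (f 0, w 0.10, h 1.02) the result is (0.81 + 0.102)/0.91 = 100.2%.

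**Denominator alone, by a second route.** Let W be the share withdrawn, q the share of these found dead, m the mean years from death to the middle of the window, and T the mean true possible years. The excess as a share of total possible time is Wqm/(T + Wqm). With T = 2.5 (all inputs assumed):
- W 5%, q 20%, m 1: 0.01/2.51 = 0.40%
- W 10%, q 20%, m 1: 0.02/2.52 = 0.79%
- W 10%, q 30%, m 1.5: 0.045/2.545 = 1.77%
- W 15%, q 30%, m 1.5: 0.0675/2.5675 = 2.63%

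Both routes give the same order of size.

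**The case against.** The strongest reply is that this is one descriptive table and that lost follow-up is handled elsewhere. That is correct. No test uses possible follow-up time. Section 7.2.2 plans a tipping-point analysis for MACE that varies the event rate of prematurely censored subjects from zero to infinite, separately by arm. Section 6.2.2 also reports total follow-up time, counts with known and unknown CV and vital status, survival by completion status, and a Kaplan-Meier plot of withdrawal. This limits the importance of the point but does not make the percentage right.

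Four stronger readings are tempting and are not supported:

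- *The percentage is simply wrong, or can never reach 100%.* The distortion needs such subjects to occur. Section 10.6.4.1 has a date-imputation rule for deaths after premature withdrawal, so the SAP expects some, but it gives no count. The two errors also offset each other.
- *Observed time is uncapped throughout.* On-treatment time is limited by the primary censoring date. The CV period ends at completion or withdrawal, with later deaths the only exception. The open end concerns vital status and those deaths.
- *A death after withdrawal makes the CV outcome fully known.* It does not. Non-fatal MI and stroke between withdrawal and death are not ascertained, and Section 10.6.2.1 lists withdrawn subjects as having unknown CV status. A CV percentage below 100% is right for them.
- *The distortion favours one arm.* It could differ by arm, but nothing in the SAP shows that it does.

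**Conclusion.** The point holds for the vital-status percentage. The SAP lets possible time run past a death that it elsewhere treats as known, and it puts no limit on observed time for withdrawn subjects traced alive. Followed exactly, the rules understate the percentage for the former and overstate it for the latter.

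The actual size cannot be obtained from the document. The 0.05 to 2.6 points rest wholly on the assumed withdrawal and death shares, and also on reading the percentage as observed over possible time and on equating completion with death for on-study deaths. The consequence is confined to a descriptive summary and its repeat under Section 8.6. The co-primary conclusions are not affected, and the point is minor.

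**What to change.** In the possible follow-up definition of Section 10.6.2:

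1. End possible follow-up at the earlier of the known death date and the study completion date, with the middle of the end-of-study window replacing the completion date for non-completers.
2. State that the completion date of a subject who dies on study is the death date.
3. For the vital-status percentage, cap observed time at that same end date.
4. For the CV-endpoint percentage, end observed time at study withdrawal even when a later death is included as an event, so that time without MI and stroke ascertainment is not counted as followed.

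The on-treatment period needs no new cap. The cost is a few lines of text and a small change to one derivation. No new data are needed, and no inferential analysis changes.
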